In the treatment arm of the study, subjects we will give sucrase at standard dose, 1 mL (8,500 I.U.) (one full measuring scoop or 28 drops) per meal or snack for patients up to 15 kg in body weight. 2 mL (17,000 I.U.), for a total of 4 weeks and follow patients recording stool frequency and consistency, emesis, weight, ability to advance enteral nutrition. Possible adverse effects of sucrase administration will also be recorded in addition to parental or patient perception of tolerance of feeds while on sucrase.

Give sucrase by g-tube or orally for 4 weeks

Record daily:

Stool frequency and consistency

Side effects on sucrase – blood sugar checks by finger stick and any new symptoms –
nausea, headache, etc

Emesis

Record weekly:

Ability to advance feeds

Abdominal circumference

Weight

Patient or parent perception of tolerance of feeds on sucrase by telephone questionnaire

ONE WEEK WASH OUT – no recordings

Give placebo by g-tube or orally for 4 weeks

Record daily:

Stool frequency and consistency

Side effects on sucrase – blood sugar checks by finger stick and any new symptoms –
nausea, headache, etc

Emesis

Record weekly:

Ability to advance feeds

Abdominal circumference

Weight

Patient or parent perception of tolerance of feeds on sucrase by telephone questionnaire

Possible additional tests:

Some patients will undergo blood test for genetic testing if available, those who have been scheduled for an endoscopy, for other medically indicated reasons as decided by the medical team, will have biopsies taken to rule out CSID.

Patients who consent to breath test for functional sucrase deficiency will have testing done.

Procedures:

SucraID™ (sucrase) administration:

Subject will be asked to take sucrase either orally or through g-tube with feeds daily and will be provided with this medication at no cost. Subjects will take sucrase or placebo each for 4 weeks so they will be taking additional medication daily for 8 weeks as they participate in the study.

Sucrose breath test:

This is an optional test for children over 4 years old that can cooperate by drinking a solution containing sucrose (sugar water) and breathing into a device to record components of their breath. The test will be offered free of charge to subjects in the study. This test is performed at home and the kit can be mailed back to us. The mailing costs are pre-paid. Inability to perform breath test will not eliminate subject from the study.

Endoscopy:

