Outcome Measure Description: Improved digestion will be assessed by number of emesis per day
Outcome Measure Timeframe: Baseline to Week 9
- Outcome Measure Title: Improved Digestion
Outcome Measure Description: Improved digestion will be assessed by change in stool consistency from hard to formed to semi solid to liquid with pieces to only liquid observed daily
Outcome Measure Timeframe: Baseline to Week 9

9) Adverse Events

a) Definition of AEs

Reported adverse events are minor and rare with Sucraid (sucrase) and overdose has not been described. In clinical studies the adverse experiences were as follows: abdominal pain, vomiting, nausea, diarrhea, constipation, insomnia, headache, nervousness, and dehydration.

b) Definition of SAEs

In one study, one asthmatic child experienced a serious hypersensitivity reaction (wheezing) probably related to sacrosidase. The event resulted in withdrawal of the patient from the trial but resolved with no sequelae.

c) Time Period and Frequency for AE assessment and Follow-up

During weekly phone calls we will assess for worsening symptoms, including but not limited to the AE as listed above

d) Adverse Event Reporting

All adverse events as defined by the FDA will be recorded by study team and reported in the results section of the study and publications.

e) Serious Adverse Event Reporting

All adverse events as defined by the FDA will be recorded by study team and reported in the results section of the study and publications. Subjects will be withdrawn as necessary if SAE occurs during study period.

10) Data and Specimen Banking

Data will be kept on a secure drive and only be accessed by the study team members. Data will be de-identified prior to data entry.

Specimens taken for pathology (for other medically indicated reasons) will be kept in patients private medical record as usual.

11) Data Management

Statistics will be done in compliance with HIPAA regulations on de-identified data.

Data will be stored on a secure drive and only accessible to study team members during and after the study.

Data will be kept post collection in compliance with regulations.

12) Risks to Subjects

Sucrase may cause a serious allergic reaction.

Blood glucose levels may change after taking sucrase – each patient already has monitor to check daily sugars while on therapy.

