Some patients treated with sucrase may have worse abdominal pain, vomiting, nausea, or diarrhea. Constipation, difficulty sleeping, headache, nervousness, and dehydration have also occurred in patients treated with sucrase.

Patients will only undergo endoscopy with biopsy if there is another medical indication as decided by the primary medical team (not the study team). Thus this risk does not pertain to the study.

13) Potential Benefits to Subjects

The most significant sources of morbidity and mortality in children with SBS are catheter related blood stream infections and parenteral nutrition-associated liver disease. Strategies that advance enterally feeding thus eliminating need for parenteral nutrition and thus central venous catheters can significantly improve outcomes in short bowel population.

14) Participant Discontinuation/ Withdrawal from the study

Participants may be discontinued if:

- They have bacteremia during course of study period and require IV antibiotic administration.
- They experience SAE or an AE that prevents them from continuing medication.
- They are admitted to the icu or hospital and made NPO during study period
- They undergo an unplanned surgery or procedure requiring them to be NPO for more than 12 hours
- They are switched by medical team to a diet not containing sucrose.
- They are no longer willing to participate in study

We will attempt to replace the withdrawn participant with another subject.

Any data collected on withdrawn subjects will be removed for purposes of statistical analysis.

15) Vulnerable Populations

NIL

16) Setting

Jackson Memorial Health system/University of Miami

17) Resources Available

[name], Assistant Professor of Pediatrics, Pediatric GI and Nutrition Specialist who runs the nutrition program at UM and Jackson that treats many patients with SBS. She has published articles on topic of SBS.

[name], Assistant Professor of Pediatrics, Pediatric GI and Short Bowel Syndrome Specialist who heads the Intestinal Rehabilitation and Intestinal Transplant service at Jackson and UM. She has published and presented data related to care of SBS for several years in many international meetings.

[name], Professor of Pediatrics, Division Chief of Department of Pediatric GI, well-published, world-renowned Pediatric GI specialist and also prior consultant on use of sucrase in patients with sucrase deficiency.

18) Prior Approvals

NIL

19) Recruitment Methods

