We will obtain approval through the institutional review board (IRB) at University of Miami and Jackson Health system. We will recruit patients, both adult and pediatric, through our Intestinal Rehabilitation Program at their regular clinic appointments in conjunction with the medical team. SGS is a rare disease and the list of patients with this condition that may meet criteria for this study is short. They will be approached in clinic by the primary medical team who follow these patients regularly. Patients will be consented in keeping with regulations of

the IRB. Only after recruitment and consent to participate in study will study access the medical records of the patients with their consent.

20) Local Number of Subjects

10 subjects

21) Confidentiality

Data, documents, reports, scans, specimens, etc. (not including consent documents) will be kept locally in a manner that is :

- Identifiable – provides least amount of protection
- De-identified and coded with the link between code and subject's identity maintained separately from the data.
- De-identified with no link to subject's identity

How will specimens obtained for this research be maintained?

- Identifiable – provides least amount of protection
- De-identified and coded with the link between code and subject's identity maintained separately from the data.
- De-identified with no link to subject's identity

If data or specimens will be coded, who will have access to the code sheet?

- Principal Investigator at UM/JHS
- Sponsor/funding entity
- Other, specify:

Data will be collected and stored on UM redcap and One Drive and will be password protected with password only known to specific members of the study team.

Paper Records (e.g., consent forms, data files, medical records, etc.): Paper files related to human subjects participation in research will be securely stored on campus. Access to files will be restricted to key personnel and supervised by the principal investigator(s) of the study. They will be kept in a secured office only accessible to PI.

Digital Records (e.g., electronic files etc.): Digital files containing human subjects research data will be stored in password protected files, on University maintained servers with regular and secured back-up. Sensitive data will also be encrypted, stored, and securely erased when appropriate.

Only the study team will have access to data.

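### Section 14 removes all data of withdrawn subjects from the analysis, leaving a completers-only crossover open to selection bias that replacement does not cure

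*Protocol*

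**What the plan says.** Section 14 lists six grounds on which a participant may be discontinued. They include "They experience SAE or an AE that prevents them from continuing medication", "They are switched by medical team to a diet not containing sucrose" and loss of willingness to take part. The others are bacteremia needing IV antibiotics, admission with NPO status, and an unplanned surgery or procedure with prolonged NPO. The section then says "We will attempt to replace the withdrawn participant with another subject" and "Any data collected on withdrawn subjects will be removed for purposes of statistical analysis".

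Other sections bear on this:
- Section 5 describes a placebo-controlled crossover in which each subject is their own control. Section 20 plans 10 subjects.
- Section 8 names stools per day, symptom score, growth velocity and enteral advancement as primary outcomes. Emesis is a secondary outcome.
- Section 12 warns: "Some patients treated with sucrase may have worse abdominal pain, vomiting, nausea, or diarrhea".
- Section 9a says: "Reported adverse events are minor and rare with Sucraid (sucrase) and overdose has not been described".
- Section 19 says: "SGS is a rare disease and the list of patients with this condition that may meet criteria for this study is short".

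No section returns withdrawn subjects to an efficacy analysis.

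**The concern.** The removal rule selects the analysed subjects on an event that occurs after treatment starts. In a crossover, withdrawal in either period deletes that subject from both. Bacteremia and unplanned surgery are unlikely to depend on the product. An adverse event that stops medication, a switch to a sucrose-free diet and unwillingness to continue can depend on it. Worse diarrhea or vomiting on a product is both a possible reason to withdraw and a bad value of a study outcome, so the rule can delete the bad outcomes themselves.

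The trial is small. One or two withdrawals are 1/10 = 10% or 2/10 = 20% of those enrolled, or 1/11 = 9% or 2/12 = 17% if each is replaced. Replacement restores the number of completers but not the comparison, because replacements are kept under the same rule. The short list of eligible patients means that replacement may also fail. From the completers' result alone, a reader could not tell which way the bias runs.

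**Working it through.** The protocol gives no alpha, power, SD or withdrawal rate, so there is no stated figure to reproduce. Everything below is illustration under assumptions.

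**Assumptions.** No true effect. Outcomes S (sucrase) and P (placebo) are normal with SD 1 and within-subject correlation r = 0.3, 0.5 or 0.7; higher is worse. The paired difference is D = P - S. A share p withdraws on sucrase only. The paired t-test is two-sided at 5%, so the nominal false-positive rate in favour of sucrase is 2.5%. Withdrawal occurs when W = kS + sqrt(1 - k^2)Z exceeds its upper-p quantile c, with Z independent standard normal noise. k = 1 is the upper end (fully outcome-driven); k = 0.5 is moderate.

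**Step 1: bias of the completers-only rule.** Shift = k(1 - r)phi(c)/(1 - p), where phi is the normal density. At p = 0.20, c = 0.842, phi(c) = 0.280 and 0.280/0.80 = 0.350. For k = 1 and r = 0.3 this gives 0.7 x 0.350 = 0.245. False-positive rates are simulated (60,000 trials per cell, enrolling until there are 10 completers).

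| p = 20%, sucrase only | r = 0.3 | r = 0.5 | r = 0.7 |
|---|---|---|---|
| k = 0.5: shift (SD) | 0.122 | 0.087 | 0.052 |
| k = 0.5: false positives | 4.7% | 4.2% | 3.8% |
| k = 1: shift (SD) | 0.245 | 0.175 | 0.105 |
| k = 1: false positives | 8.8% | 7.4% | 5.7% |

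At 10% and 30% withdrawal the upper-end shifts are 0.06-0.14 and 0.15-0.35 SD. The table already assumes full replacement; without replacement the shifts are the same. Equal withdrawal on both products gives a shift of 0.00. Withdrawal on placebo only gives the mirror image, against sucrase.

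**Step 2: what retaining the data achieves (k = 1).** If the outcome that drives withdrawal is fully recorded, the residual shift is at most about 0.02 SD for withdrawal in either period. If withdrawal is in the first period and the record captures only half the excess, retained data leave 0.03-0.14 SD, a reduction of 51-61% against completers-only.

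**Step 3: the unfavourable case.** Withdrawal is in the second period, is driven by that period's outcome, and the record captures half the excess. The retained-data shift is then phi(c)/2 whatever r is: 0.1755/2 = 0.088, 0.280/2 = 0.140 and 0.348/2 = 0.174 SD at p = 10, 20 and 30%. Dividing by the completers-only shift gives the ratio (1 - p)/[2(1 - r)]:
- r = 0.3: 0.9/1.4 = 0.64, 0.8/1.4 = 0.57, 0.7/1.4 = 0.50. Retaining helps.
- r = 0.5: 0.90, 0.80, 0.70. It helps less. Simulation gives reductions of 7, 19 and 28%.
- r = 0.7: 0.9/0.6 = 1.50, 0.8/0.6 = 1.33, 0.7/0.6 = 1.17. It is worse. Simulation gives 49, 32 and 15% more bias (0.09-0.17 against 0.06-0.15 SD), with error in the biased direction of about 5-13% against 4-8%.

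The formula and simulation differ slightly because the simulated trials stop at exactly ten completers.

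**The case against.** **Few withdrawals.** Section 9a expects minor and rare adverse events, and section 14 makes discontinuation permissive rather than automatic. At 10% withdrawal with k = 0.5, false positives are 3.2-3.7%, a small excess. This stands as a limit on size. It does not justify deleting the data of whoever does withdraw, and discretion over withdrawal can itself add selection.

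**Partial overlap.** The listed sucrase effects match two of the four primary outcomes (stools, symptoms) and one secondary outcome (emesis). Growth velocity and enteral advancement are not among them. This stands, and the claim is limited accordingly.

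**Matter for the SAP.** The layout of withdrawal tables can be left there. The removal rule cannot, because the protocol states it and a SAP that kept the data would contradict it.

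**Safety reporting.** A reader might infer that adverse events of withdrawn subjects will disappear from the report. The protocol does not support that: sections 9d and 9e require all adverse events to be recorded and reported, and the removal sentence concerns statistical analysis. Adverse-event withdrawals would thus be partly visible, but their efficacy data would still be missing.

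**Larger figures.** A reader might also remove the 1, 2 or 3 of 10 subjects with the worst sucrase-minus-placebo difference and obtain two-sided error of about 10, 19 or 31%. That assumes withdrawal picks out exactly those subjects, which nothing in the protocol indicates.

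**Conclusion.** The point holds as a vulnerability created by a written rule and should be fixed. Followed as worded, section 14 yields a completers-only comparison that is open to selection bias towards the product with the outcome-driven withdrawals.

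It may be tempting to conclude that the result will favour sucrase. The documents do not support this. They give no withdrawal rates by product; withdrawals driven by poor outcomes on placebo would bias against sucrase, and equal rates would leave about zero bias. Nor do they support any particular size: the 20% rate, the restriction to one product, the correlations and the strength of the link to outcome are all assumed. Under them the effect runs from modest to material for a trial of ten. It is also too strong to say that retaining data always reduces bias, since step 3 shows a plausible case where it does not.

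**What to change.** Replace the removal sentence in section 14 with:

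> Data collected up to withdrawal are retained. The primary analysis includes every subject who received any study product, using all available period data; a completers-only analysis is shown alongside it. The number, product, period and reason of withdrawals are reported.

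State also that replacements are added to the withdrawn subjects and not substituted for them. The grounds for discontinuation need no change. Data up to withdrawal will exist, because section 7 already has the team "follow patients recording stool frequency and consistency, emesis, weight, ability to advance enteral nutrition" at daily or weekly intervals.

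The cost is one paragraph of wording, a little more analysis work and a possibly less favourable result. The gain depends on how fully the deterioration before withdrawal is recorded: nearly complete with a full record, doubtful or negative with a half record late in the trial and high within-subject correlation. That is the reason to show both analyses, so that a reader can see whether the conclusion depends on the choice.
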